TAF	tenofovir alafenamide (Vemlidy®)
TEAE	treatment-emergent adverse event
TE	treatment emergent
TFFU	treatment-free follow-up
TFLs	tables, figures, and listings
ULN	upper limit of normal
WHO	World Health Organization

PHARMACOKINETIC ABBREVIATIONS

λz terminal elimination rate constant, estimated by linear regression of the terminal elimination

phase of the log concentration of drug versus time curve of the drug

 $\% AUC_{exp}$ percentage of AUC extrapolated between AUC_{last} and AUC_{inf}

 AUC_{last} area under the concentration versus time curve from time zero to the last quantifiable

concentration

AUC_{inf} area under the concentration versus time curve extrapolated to infinite time, calculated as

 $AUC_{last} + \left(C_{last}/\lambda_z\right)$

AUC₀₋₂₄ partial area under the concentration versus time curve from time "0" to time "24"

CL/F apparent oral clearance after administration of the drug:

 $CL/F = Dose/AUC_{inf}$, where "Dose" is the dose of the drug

C_{last} last observed quantifiable concentration of the drug

C_{max} maximum observed concentration of drug

 $t_{1/2}$ estimate of the terminal elimination half-life of the drug, calculated by dividing the natural log of

2 by the terminal elimination rate constant (λ_z)

 T_{last} time (observed time point) of C_{last} T_{max} time (observed time point) of C_{max}

1. INTRODUCTION

This statistical analysis plan (SAP) describes the statistical analysis methods and data presentations to be used in tables, figures, and listings (TFLs) in the clinical study report (CSR) for Study GS-US-465-4439. This SAP is based on the study protocol amendment 2 dated 12 April 2023 and the electronic case report form (eCRF). The SAP will be finalized before the Primary Analysis at Follow-up (FU) Week 24 when all participants complete Follow-Up (FU) Week 24 or early terminated from the study prior to FU Week 24, and will be used for both Primary Analysis and Final Analysis. Any changes made after the finalization of the SAP will be documented in the CSR.

1.1. Study Objectives and Endpoints

The proportion of participants who achieve functional cure, defined as HBsAg loss and HBV DNA < LLOQ at FU Week 24	
functional cure, defined as HBsAg loss and	
Secondary Endpoint(s)	
 The proportion of participants with HBsAg loss with and without anti-HBsAg seroconversion during the study The proportion of participants with HBeAg loss with and without anti-HBeAg seroconversion during the study in participants with CHB who are HBeAg positive at baseline The proportion of participants who remain off NUC treatment during FU The proportion of participants experiencing HBV virologic breakthrough during study treatment(s) as defined in protocol Section 2. 	

1.2. Study Design

Approximately 40 NUC-suppressed and 60 viremic CHB-infected participants may be enrolled and assigned into a cohort below. Each cohort will enroll a minimum of 20% of HBeAg-positive participants, and up to 20% of participants can have HBsAg \leq 100 IU/mL.

NUC-suppressed Cohort

Cohort 1 (n = 40):

- TAF 25-mg tablet administered orally once daily for 36 weeks
- VIR-2218 200 mg administered via SC injection once every 4 weeks for 24 weeks (total 6 doses)

At Week 12, add-on and initiate the below treatment:

- SLGN 3 mg (2 × 1.5-mg tablets) administered orally while fasting once a week on the same day for 24 weeks (total 24 doses)
- Nivolumab 0.3 mg/kg administered IV once every 4 weeks for up to 24 weeks (up to 6 doses)

Viremic Cohort

Cohort 2 (n = 60)

Participants will be randomized 2:1 into Cohort 2 (Groups A and B) and stratified by HBsAg > or \leq 3 log₁₀ IU/mL.

Group A (n = 40):

• VIR-2218 200 mg administered via SC injection once every 4 weeks for 24 weeks (total 6 doses)

At Week 12, add-on and initiate the below treatment:

- SLGN 3 mg (2 × 1.5-mg tablets) administered orally while fasting once a week on the same day for 24 weeks (total 24 doses)
- Nivolumab 0.3 mg/kg administered IV once every 4 weeks for up to 24 weeks (up to 6 doses)

[figure not shown]
Group B (n = 20):

- SLGN 3 mg (2×1.5 -mg tablets) administered orally while fasting once a week on the same day for up to 24 weeks (up to 24 doses)
- Nivolumab 0.3 mg/kg administered IV once every 4 weeks for up to 24 weeks (up to 6 doses)

After completing study treatments all participants will enter the FU period.

Figure 1-1 provides the study design schema.

Figure 1-1. Study Design Schema*

IV = intravenous; NUC = nucleos(t)ide(s); PO = oral; Q4W = every 4 weeks; QD = once daily; QW = every week; SLGN = selgantolimod; SC = subcutaneous; TAF = tenofovir alafenamide

- a Viremic participants who meet criteria to initiate NUC treatment will receive TAF 25 mg once daily for up to 36 weeks during the study.
- b SLGN dosed while fasting once a week, on the same day, for 24 weeks.
- c Participants will continue to receive TAF per Protocol Section 3.5.
- * NOTE: Nivolumab dosing was stopped in this study and all treatments in Cohort 2 Group B were discontinued. This was a sponsor decision based on a benefit risk assessment on the use of nivolumab in HBV cure. Rationale is provided in Protocol Section 1.3.1.

Additional details regarding study assessments can be found in Appendix 1.

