1.2.1. Changes to Study Design

Nivolumab dosing was stopped by Gilead as part of benefit-risk assessment based on emerging safety data from this study, other studies evaluating anti-PD-1/PD-L1 mAbs, and pertinent patient and prescriber insights {Cohen C. 2020}. As the study had completed enrollment and all participants were undergoing study treatment when the decision was made to stop nivolumab administration, the following measures were implemented:

- Stopped further nivolumab administration for all study participants across all cohorts
- Continued treatment with VIR-2218 and SLGN through Week 36 for Cohort 1 and Cohort 2 Group A
- Discontinued all study treatment for Cohort 2 Group B participants
- Stopped all sample collections related to nivolumab
- NUC treatment cessation was no longer required for NUC treated participants (Cohort 1)

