3.8.2. Analysis Visit Windows

Participant visits might not occur on protocol-specified days. Therefore, for the purpose of analysis, observations will be assigned to analysis windows as specified in Table 3-1 to Table 3-12.

Data collected up to the last on-treatment date + 3 days will be considered as on-treatment data, whereas data collected afterwards will be considered as follow-up data.

For each drug, the last on-treatment date is defined as follows:

- Last on-treatment date for VIR-2218 = (last injection date of VIR-2218 + 28 days) -1
- Last on-treatment date for nivolumab = (last injection date of nivolumab + 28 days) 1
- Last on-treatment date for selgantolimod = (last dose date of selgantolimod + 7 days) -1

For Cohort 1 and Cohort 2 Group A, the composite last on-treatment date is the latest date of the last on-treatment date of VIR-2218, nivolumab, or SLGN.

For Cohort 2 Group B, the composite last on-treatment date is the latest date of the last on-treatment date of nivolumab or SLGN.

Participants are allowed to continue taking TAF after the discontinuation of study treatments, hence TAF will not be considered for constructing the analysis windows.

The follow-up day (FU Day) in Posttreatment tables is defined as:

• FU Day = Assessment date – composite last on-treatment date.

A baseline value is defined as the last available value collected on or prior to the date of first dose of any study drug. An unscheduled visit prior to the first dosing of study drug will be included in the calculation of the baseline value, if applicable.

The analysis windows for on-treatment assessments are provided in Table 3-1 to Table 3-9. Table 3-10 to Table 3-12 provide analysis windows for posttreatment assessments.

Table 3-1. Cohort 1 and Cohort 2 Group A: Analysis Visit Windows for On-treatment Vital Signs, Hematology, Chemistry, Coagulation, Quantitative Plasma HBV DNA, Quantitative HBV (serum HBsAg, HBcrAg, HBeAg, and HBV RNA), Qualitative HBV Serology (HBeAg, hepatitis B e antibody (HBeAb), HBsAg, and hepatitis B surface antibody (HBsAb))

		Visit Window Study Day	
Visit	Study Day	Lower Limit	Upper Limit
Baseline	1	(none)	1
Week 4	29	2	43
Week 8	57	44	71
Week 12	85	72	92
Week 14	99	93	106
Week 16	113	107	127
Week 20	141	128	155
Week 24	169	156	183
Week 28	197	184	211
Week 32	225	212	239
Week 36	253	240	≥ 253

Table 3-2. Cohort 1 and Cohort 2 Group A: Analysis Visit Windows for On-treatment Urinalysis

		Visit Windo	w Study Day

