7.4.2. Concomitant Medications

Concomitant medications are defined as medications taken while a participant took study drug. Use of concomitant medications will be summarized by preferred name using the number and percentage of participants for each treatment group. A participant reporting the same medication more than once will be counted only once when calculating the number and percentage of participants who received that medication. The summary will be ordered by preferred term in descending overall frequency. For drugs with the same frequency, sorting will be done alphabetically.

For the purposes of analysis, any medications with a start date prior to or on the first dosing date of study drug and continued to be taken after the first dosing date or started after the first dosing date but prior to or on the last dosing date of study drug will be considered concomitant medications. Medications started and stopped on the same day as the first dosing date, or the last dosing date of study drug will also be considered concomitant. Medications with a stop date prior to the date of first dosing date of study drug or a start date after the last dosing date of study drug will be excluded from the concomitant medication summary. If a partial stop date is entered, any

medication with the month and year (if day is missing) or year (if day and month are missing) prior to the date of first study drug administration will be excluded from the concomitant medication summary. If a partial start date is entered, any medication with the month and year (if day is missing) or year (if day and month are missing) after the study drug stop date will be excluded from the concomitant medication summary. Medications with completely missing start and stop dates will be included in the concomitant medication summary, unless otherwise specified. Summaries will be based on the Safety Analysis Set. No formal statistical testing is planned.

All prior and concomitant medications (other than per-protocol study drugs) will be provided in a by-participant listing sorted by participant ID number and administration date in chronological order.

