Sparse PK for VIR-2218 ⁿ		X			X				X													
Sparse PK for SLGN ⁿ					X				X			X										
Estimated creatinine clearance (using the Cockcroft-Gault method)	X	X			Х								Х	X								Х
Urinalysis	X	X	X	X	X			X	X	X	X	X	X	X								
Urine Drug and Alcohol Screen	X																					
Autoantibodies	X																					
TSH	X									X			X	X								
FSH ^o	X																					
Serum Pregnancy TestP	X													Х								
Urine Pregnancy Test ^p		Х	Х	Х	Х			Х	Х	X	X	X	X			X	Хр	Х	Хр	X	X	Х
Enrollment		X																				
Dispense and Administer TAF as appropriate						7	Tenofo	vir ala	fenam	ide (T	TAF) 2	25-mg t	ablet adminis	stered or	ally da	ly for u	p to 84	weeks				

	Screening	Baseline		,	Treat	ment (Cycles	Wee	ek (± 2	2 days	s) a		EOT (-5 days)				F	ollow-ı	ıp Weel	ks ^b		
	(45 days)	Day 1	4	8	12	13 ^c	14	16	20	24	28	32	36/EOT	EDd	1¢	4	8c	12	16 ^c	24	36	48
Dispense & Administer VIR-2218 SC as appropriate		X	X	X	X			X	X													
Dispense & Administer SLGN9 as appropriate					X	X	Х	Х	X	X	X	X										
Study Drug Accountability			X	X	X		X	X	X	X	X	X	X									

AE = adverse event; APRI = AST to Platelet Ratio Index; CT = computed tomography; ddPCR = digital droplet polymerase chain reaction; ECG = electrocardiogram; ED = early discontinuation; EOT = end of treatment; FSH = follicle-stimulating hormone; FU = follow-up; HBcAg = hepatitis B core-related antigen; HBeAb = hepatitis B e antibody; HBeAg = hepatitis B e antigen; HBv = hepatitis B virus; HCC = hepatocellular carcinoma; HCV = hepatitis C virus; HDV = hepatitis D virus;

IV = intravenous; PBMC = peripheral blood mononuclear cells; PK = pharmacokinetic; SAE = serious adverse event; SC = subcutaneous; SLGN = selgantolimod; TAF = tenofovir alafenamide;

TSH = thyroid-stimulating hormone

- a All study visits except for Weeks 13 and 14.
- b FU Week 1 will have a visit window of + 3 days, FU Weeks 4 through FU Week 16 will have a visit window of ± 5 days, and FU Weeks 24 through FU Week 48 will have a visit window of ± 14 days.
- c Week 13, FU Week 8, and FU Week 16 will be conducted as a virtual/telephonic visit to review AEs, concomitant medications, and overall health of the participant by investigator.
- d The ED visit should be performed within 14 days from notification of study discontinuation. If ED is done in FU period, all of these procedures should be performed.

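### Two rules do not carry over the exclusion of TAF: a late adverse event can be both treatment-emergent and non-treatment-emergent, and the concomitant-medication window can end at Day 246 or Day 588 (minor)

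*SAP*

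**What the plan says.** **TAF duration.** The Cohort 1 design bullet in Section 1.2 reads "TAF 25-mg tablet administered orally once daily for 36 weeks". In Appendix Table 1 the row "Dispense and Administer TAF as appropriate" gives daily dosing for up to 84 weeks. A footnote to the design figure adds: "Participants will continue to receive TAF per Protocol Section 3.5". Section 1.2.1 says that stopping NUC treatment was no longer required in Cohort 1. For Cohort 2 another footnote says: "Viremic participants who meet criteria to initiate NUC treatment will receive TAF 25 mg once daily for up to 36 weeks during the study".

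**Status of TAF.** Section 4.2 handles TAF as a study drug for exposure and adherence. Section 7.1.3 names it among the study treatments to which relatedness is assessed.

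**Where TAF is excluded.** Section 3.8.2 notes that TAF may continue after study treatments stop, "hence TAF will not be considered for constructing the analysis windows". For Cohort 1 and Group A, "the composite last on-treatment date is the latest date of the last on-treatment date of VIR-2218, nivolumab, or SLGN".

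**Adverse-event classes.** Section 7.1.6.1 makes an event treatment-emergent on either of two grounds:
- onset between first dose and the composite date + 30 days; or
- the event led to early stopping of any study drug, with no date limit.

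Section 7.1.6.2 defines the non-treatment-emergent class only by onset after the composite date + 30 days.

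**Concomitant medication.** Under Section 7.4.2, medication with "a start date after the last dosing date of study drug will be excluded from the concomitant medication summary". The section does not say which drug's last dose is meant, and it does not refer to the composite date.

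**The concern.** The SAP recognises that TAF can outlast the other drugs and removes it from the visit windows and the composite date. The same step is missing in two places where it is also needed.

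The treatment-emergent and non-treatment-emergent tables (7.1.7.1 and 7.1.7.2) are meant to divide events between the treatment period and the time after it. If one event can satisfy both definitions, it appears in both tables and the division fails.

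In 7.4.2 the end of the observation period depends on whether TAF counts as study drug. If it does, the percentages in adjacent columns cover very different lengths of time. Within Cohort 2 the length can also depend on whether a participant started TAF after baseline, which is a post-randomisation event. Two programmers could reasonably produce different tables from the same text.

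**Working it through.** **Inputs, all from the SAP's planned schedule.** Cohort 1 and Group A: VIR-2218 every 4 weeks from Day 1 (6 doses), SLGN weekly from Week 12 = Day 85 (24 doses), nivolumab every 4 weeks from Day 85 (up to 6 doses). Group B: SLGN weekly (up to 24 doses) and nivolumab every 4 weeks (up to 6 doses), both from Day 1. Follow-up: 48 weeks.

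**The 84 weeks.** 36 weeks of treatment + 48 weeks of follow-up = 84 weeks. The two TAF statements thus match the treatment period and the treatment period plus follow-up.

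**Last planned dose.**
- SLGN, Cohort 1 and Group A: 85 + 23 × 7 = Day 246
- SLGN, Group B: 1 + 23 × 7 = Day 162
- VIR-2218: 1 + 5 × 28 = Day 141
- Nivolumab: 85 + 5 × 28 = Day 225 (Cohort 1, Group A); 1 + 5 × 28 = Day 141 (Group B)
- TAF, Cohort 1: 84 × 7 = Day 588, or 36 × 7 = Day 252 if cut at the treatment period

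**Treatment-emergent date window.** Composite date in Cohort 1 and Group A: the latest of 246 + 7 − 1 = 252, 225 + 28 − 1 = 252 and 141 + 28 − 1 = 168, so Day 252. The cutoff is 252 + 30 = Day 282. Group B: the later of 162 + 6 = 168 and 141 + 27 = 168, so the cutoff is 168 + 30 = Day 198. TAF enters none of these.

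**Overlap of the two classes.** For a Cohort 1 participant on TAF to Day 588, the span after the cutoff is 588 − 282 = 306 days. An event with onset in that span is non-treatment-emergent by 7.1.6.2. If it stops TAF and is recorded as premature discontinuation of study drug, it is also treatment-emergent by the second ground of 7.1.6.1. The other three drugs have had their last dose before the cutoff, so TAF is the drug through which the overlap arises.

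**Concomitant window under three readings of 7.4.2.**

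| Reading | Cohort 1 ends | vs Group A (Day 246) | vs Group B (Day 162) |
|---|---|---|---|
| TAF counts to Week 84 | Day 588 | 588/246 = 2.39 | 588/162 = 3.63 |
| TAF counts to Week 36 only | Day 252 | 252/246 = 1.02 | 252/162 = 1.56 |
| TAF does not count | Day 246 | 246/246 = 1.00 | 246/162 = 1.52 |

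The Group A and Group B columns assume no TAF.

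**Cohort 2 with TAF.** Suppose a Group A participant starts 36 weeks of TAF at Week 12, 24 or 36 (assumed starts; the SAP gives none). If that TAF counts, the window ends at Day (12 + 36) × 7 = 336, (24 + 36) × 7 = 420 or (36 + 36) × 7 = 504, instead of Day 246.

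**The case against.** Three stronger readings are tempting, and the documents do not support them.

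*That TAF lengthens the treatment-emergent window.* It does not. The window closes at the composite date + 30 days, and that date is built without TAF.

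*That 36 and 84 weeks are a plain contradiction.* The design-figure footnote, Section 1.2.1 and Section 3.8.2 all point to TAF continuing in follow-up, and 36 + 48 = 84 fits that. What remains is a design bullet without a cross-reference.

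*That 7.4.2 expressly counts follow-up TAF.* It neither names nor excludes TAF. Other sections confine it: exposure is cut at the treatment period (4.2.1), adherence runs to Week 36 (4.2.2.1), disposition tracks TAF for Cohort 1 in the treatment phase only (4.1), and the drug-specific event summaries omit it (7.1.7.1). On that pattern the Cohort 1 and Group A windows differ by 6 days. The disposition rule also makes it uncertain that stopping TAF in follow-up would be recorded as premature discontinuation.

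It is also fair to say that these tables are descriptive, that Cohort 1 is not randomised against Cohort 2, and that Groups A and B already differ by design (Day 246 against Day 162).

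This narrows the point without removing it. Where the authors wanted TAF truncated, they said so; 7.4.2 and the second ground of 7.1.6.1 contain no such limit. Section 3.8.1, which takes the last dose from the permanent-withdrawal record, makes no exception for TAF either.

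**Conclusion.** The point holds in a limited form and is minor.

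- The two adverse-event definitions can overlap. This needs a participant still on TAF after the composite date + 30 days, an event that stops TAF, and a record of premature discontinuation. How often that occurs cannot be told from the SAP.
- The end of the concomitant window is not fixed with respect to TAF. On the literal reading it can reach Day 588 in Cohort 1, 2.39 times Group A and 3.63 times Group B without TAF. With TAF confined to the treatment period the ratio to Group A is 1.02. Cohort 2 participants who start TAF are affected too, so the contrast is not simply Cohort 1 against the rest.

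The day counts assume full planned dosing. The early stop of nivolumab and of all Group B treatment makes the Group B figure an upper value. No efficacy endpoint, visit window or treatment-emergent date cutoff changes. Which TAF duration is right is not judged here; the passages need to be reconciled.

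**What to change.** 1. **Make the two event classes mutually exclusive.** Any one of these will do: restrict the second ground of 7.1.6.1 to stopping of SLGN, nivolumab or VIR-2218; restrict it to onset by the composite date + 30 days; or state in 7.1.6.2 that treatment-emergent events are excluded. The first two place a late TAF-stopping event in the non-treatment-emergent tables; the third keeps it in the treatment-emergent tables.
2. **Name the end date in 7.4.2.** Use either the last dose of SLGN, VIR-2218 or nivolumab, or the composite date of 3.8.2. The composite date is already defined but lengthens the window by 7 − 1 = 6 days after the last SLGN dose, or 28 − 1 = 27 days after an injection or infusion.
3. **Cross-reference** the 36-week bullet in Section 1.2 with the up-to-84-week row in Appendix Table 1, so that the reader can see which period each covers.

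The cost is a few sentences and one date variable in programming. Section 1 already provides for changes after finalisation to be documented in the CSR. The downside is that medication started in follow-up leaves the concomitant table, though it stays in the by-participant listing. The difference in window length between Groups A and B remains, because it follows from the design.

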1.2.1. Changes to Study Design

Nivolumab dosing was stopped by Gilead as part of benefit-risk assessment based on emerging safety data from this study, other studies evaluating anti-PD-1/PD-L1 mAbs, and pertinent patient and prescriber insights {Cohen C. 2020}. As the study had completed enrollment and all participants were undergoing study treatment when the decision was made to stop nivolumab administration, the following measures were implemented:

- Stopped further nivolumab administration for all study participants across all cohorts
- Continued treatment with VIR-2218 and SLGN through Week 36 for Cohort 1 and Cohort 2 Group A
- Discontinued all study treatment for Cohort 2 Group B participants
- Stopped all sample collections related to nivolumab
- NUC treatment cessation was no longer required for NUC treated participants (Cohort 1)

1.3. Sample Size and Power

2. TYPE OF PLANNED ANALYSIS

2.1. Primary Analysis

The Primary Analysis will be conducted after all participants have completed FU Week 24 or early terminated from the study prior to FU Week 24.

2.2. Final Analysis

The final analysis will be performed after all participants have completed the study, outstanding data queries have been resolved or adjudicated as unresolvable, and the data have been cleaned and finalized.

3. GENERAL CONSIDERATIONS FOR DATA ANALYSES

Analysis results will be presented using descriptive statistics. For categorical variables, the number and percentage of participants in each category will be presented; for continuous variables, the number of participants (n), mean, standard deviation (SD) or standard error (SE), median, first quartile (Q1), third quartile (Q3), minimum, and maximum will be presented.

By-participant listings will be presented for all participants in the All Enrolled Analysis Set and sorted by cohort, treatment group if applicable, and participant ID number in ascending order, visit date, and time (if applicable), unless otherwise specified. Data collected on log forms, such as AEs, will be presented in chronological order within the participant. The cohort, and treatment group if applicable, to which participants were enrolled and/or randomized will be used in the listings. Age, sex at birth, race, and ethnicity will be included in the listings, as space permits.

